5.0 Treatment Plan

5.1 Dosing

- 5.1.1 Leukapheresis to collect PBMC for infusion will be performed the day prior to infusion. Patients will be administered three infusions of APN401 at 50×10^6 cells/kg IV, separated by 4 weeks (reference Appendix I). Leukapheresis and administration of APN401 can be delayed up to 3 weeks at the physician's discretion. Subsequent treatment must occur 28 days after prior treatment.
- 5.1.2 Six patients will be treated initially. Should >1/6 subjects experience greater than grade 3 or 4 toxicity, further enrollment of study subjects and further administration of the study agent will stop pending assessment of the risk.
- 5.1.3 If DLT is observed in $\leq 1/6$, than an additional four patients (a total of 12) will be enrolled to allow evaluation of laboratory correlates. Enrollment will be suspended if >1/6 or >3/12 patients manifest DLT

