MAIN INCLUSION CRITERIA	
 Signed written informed consent Histologically confirmed metastatic or inoperable solid tumor no longer responding to standard therapies Must be at least 4 weeks since prior systemic therapy, radiation and/or surgery ECOG performance status 0-1 Hematocrit $\geq 28\%$, WBC $>3000/\mu\text{l}$, and platelets $>100,000/\mu\text{l}$ Creatinine $\leq 1.6 \text{ mg/dl}$ ALT and AST <2.5 fold the upper limit of normal and total bilirubin $\leq 1.6 \text{ mg/dl}$
MAIN EXCLUSION CRITERIA	
 Pregnant or breastfeeding patients Untreated, progressing, or symptomatic brain metastasis HIV, hepatitis B, or hepatitis C (active) infection Active autoimmune disease Ongoing requirement for an immunosuppressive treatment Significant cardiovascular or pulmonary disease
TREATMENT PLAN	
 PBMC for infusions will be collected by leukapheresis the day prior to infusion. Patients will be administered three infusions separated by 4 weeks Blood will be drawn pre-therapy and at 3, 5, 9, and 10 weeks, and then every 8 weeks for immune assessments Imaging will be performed pre-therapy and 2 weeks after infusion 3 and then every 8 weeks for clinical response Six patients will be treated initially. If a dose limiting toxicity (DLT) is observed in $\leq 1/6$, than an additional four patients will be enrolled to allow evaluation of laboratory correlates. Enrollment will be suspended if $>1/6$ or $>3/12$ patients manifest DLT
LABORATORY CORRELATES	
 PBMC cytokine response Circulating immunocytes
POPULATION SIZE	
 Two to 12 eligible and evaluable patients
STUDY DURATION	
 Patients will be followed for toxicity until objective disease progression or 1 year, whichever occurs first.

Safety and Immunologic Activity of Multiple Infusions of APN401
Wake Forest Baptist Comprehensive Cancer Center
CCCWU 03716

Contents

1.0	Background	6
1.1	Adoptive cellular immunotherapy	6
1.2	Cbl-b	6
1.3	APN401	7
1.4	Phase 1 study of single infusion of APN401	7
1.5	Study rationale	7
2.0	Objectives	8
2.1	Primary	8
2.2	Secondary	8
3.0	Selection of Patients	8
3.1	Inclusion criteria	8
3.2	Exclusion criteria	9
4.0	Patient Registration	10
5.0	Treatment Plan	11
5.1	Dosing	11
5.2	Leukapheresis	11
5.3	Infusion	11
5.4	Supportive care guidelines	12
5.5	Nursing implications	13
5.7	Duration of follow-up	14

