8.2 Dose limiting toxicity (DLT)

DLT is defined as

- 8.2.1 CTCAE grades 3-5 allergic reactions related to study cell infusion
- 8.2.2 CTCAE grades 3 and greater autoimmune reactions other than that vitiligo
- 8.2.3 CTCAE grades 3 and greater organ toxicity (cardiac, dermatologic, gastrointestinal, hepatic, pulmonary, renal/genitourinary or neurologic) not pre-existing or due to the underlying malignancy and occurring within 30 days of study product infusion
- 8.2.4 Treatment-related death within 8 weeks of the study cell infusion

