11.3.2 Sample size

A total of up to 12 patients will be treated to allow evaluation of laboratory correlates. The design allows for an interim analysis to occur after the first 6 patients are enrolled. If 1 or less experience a grade 3-4 toxicity then 4 more will be enrolled, if 3 or less experience a grade 3-4 toxicity the agent will not be considered too toxic. With this sample size, during the first stage of the trial, if the true toxicity rate is 10% (or less) the trial will stop with 11% probability, whereas if the true toxicity rate is 40% (or higher) then the trial will stop with 76.7% probability. Likewise, if the trial continues to 12 patients, if the true toxicity rate is 10% or less the probability of observing more than 3 toxicities is 1.2% and if the true toxicity rate is 40% or more then the probability of observing more than 3 toxicities is 62%.

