11.4 Analyses

Adverse events will be categorized by organ system and severity and summarized as frequency counts and percentages. Other categorical data, such as clinical response, will be summarized similarly. Measured data, such as immune response, will be summarized as medians and ranges. All tests of statistical significance will be 2-sided and p-values will generally not be adjusted for multiple comparisons.

11.4.1 **Toxicity:** APN401 will be considered tolerable if $\leq 1/6$ or if overall $\leq 3/12$ patients (i.e. an observed toxicity rate of at most 30%) experience grade 3-4 toxicity. With this design the likelihood of stopping early and rejecting the therapy as too toxic is $\leq 11.4\%$ if the true grade 3-4 toxicity rate is $\leq 10\%$ and $> 76.7\%$ if it is $> 40\%$. The overall likelihood of declaring APN401 too toxic is $\leq 1.2\%$ and $> 62\%$, respectively in these scenarios.

11.4.2 **Immune response:** APN401 will be considered immunologically active if PBMC IFN- γ production in response to anti-CD3/28 stimulation or to one or more tumor antigens is significantly increased or if neutrophil to lymphocyte ratio is significantly decreased post-therapy (week 9) compared to pre therapy. Immune responses will be summarized as medians and ranges. The effects of treatment on these markers individually will be analyzed using paired t-tests or the non-parametric counterpart. With 12 patients there will be statistical power equal to 80% to detect 1 standard deviation change in these markers following treatment. All tests will be 2-sided and $P < 0.05$ will be considered significant.

Safety and Immunologic Activity of Multiple Infusions of APN401
Wake Forest Baptist Comprehensive Cancer Center
CCCWU 03716

11.4.3 Clinical response and survival: Clinical response will be assessed by RECIST and summarized as frequency counts and percentages. Progression-free survival and overall survival are calculated from the initial infusion to confirmation of progression or death. Exploratory survival plots will be estimated using the Kaplan Meier approach and median PFS and OS will be estimated if enough events occur.

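### The 1/6 and 3/12 toxicity limits are applied to different events in different sections, so expansion and the tolerability verdict can disagree on the same patients

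*Combined protocol and SAP*

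**What the plan says.** Five places in the combined protocol and SAP use the boundary.

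- **Synopsis, Treatment plan:** "If a dose limiting toxicity (DLT) is observed in" no more than 1/6, further patients are enrolled. The event is DLT.
- **5.1.3:** the same rule, then "Enrollment will be suspended if >1/6 or >3/12 patients manifest DLT".
- **5.1.2:** enrolment and dosing both halt, pending a risk assessment, when more than 1/6 "subjects experience greater than grade 3 or 4 toxicity, further enrollment of study subjects and further administration of the study agent will stop". It has no 12-patient counterpart.
- **11.3.2:** one or fewer of six with grade 3-4 toxicity leads to enrolling four more, and "if 3 or less experience a grade 3-4 toxicity the agent will not be considered too toxic". The operating characteristics follow: "if the true toxicity rate is 10% (or less) the trial will stop with 11% probability".
- **11.4.1:** APN401 is tolerable if at most 1/6, or at most 3/12 overall, "patients (i.e. an observed toxicity rate of at most 30%) experience grade 3-4 toxicity".

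Section 8.2 defines DLT. It covers grade 3-5 allergic reactions related to the infusion, autoimmune reactions of grade 3 or more other than vitiligo, treatment-related death within 8 weeks, and "CTCAE grades 3 and greater organ toxicity (cardiac, dermatologic, gastrointestinal, hepatic, pulmonary, renal/genitourinary or neurologic) not pre-existing or due to the underlying malignancy", the last only if "occurring within 30 days of study product infusion". Section 8.1 has adverse events recorded for up to 2 months after dosing.

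**The concern.** Safety is the primary objective (2.1.1), the toxicity rate is the primary outcome (11.1.1), and this boundary is the only numerical decision rule attached to it. Sections 5.1.3 and 11.3.2 both decide whether the trial goes beyond six patients, using different events. Section 11.4.1 then delivers the verdict on the Section 11 event, although 5.1.3 suspends enrolment on DLT. With six patients and a limit of one, classifying two patients differently reverses the decision. If the definition is settled only after events are seen, the verdict becomes a matter of choice.

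**Working it through.** **1. The stated stage 1 figures.** Inputs from 11.3.2: n = 6, stop if more than 1 event, true rates 10% and 40%.

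P(stop) = 1 − (1−p)^6 − 6p(1−p)^5

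- p = 0.10: 1 − 0.5314 − 0.3543 = 0.1143
- p = 0.40: 1 − 0.0467 − 0.1866 = 0.7667

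Both reproduce (11% in 11.3.2 and 11.4% in 11.4.1; 76.7% in both). They hold for whichever event is counted, at that event's own rate. The plan states them for grade 3-4 toxicity.

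**2. The events side by side.**

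| | DLT (8.2) | Grade 3-4 toxicity (Section 11) |
|---|---|---|
| Grade 5 | included | literally excluded |
| Organ systems | seven listed groups for organ toxicity; haematologic not listed | no limit stated |
| Cause | organ toxicity must not be pre-existing or due to the cancer | none stated |
| Time | 30 days for organ toxicity, 8 weeks for death | none stated |

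Section 5.1.2 excludes grade 3 whether it is read as above grade 3 or above grade 4.

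**3. Four test cases.** Each supposes two of six patients with the event and none in the other four.

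| Event | DLT (5.1.3) | Grade 3-4 (11.3.2, 11.4.1) | 5.1.2 as written | 5.1.2 if grade 3 or greater |
|---|---|---|---|---|
| A. Grade 3 haematologic toxicity | 0/6, enrol more | 2/6, over limit | 0/6 | 2/6, halt |
| B. Treatment-related death within 8 weeks, recorded only as grade 5 | 2/6, suspend | 0/6, within limit | 2/6, halt | 2/6, halt |
| C. Grade 3 listed-organ toxicity, not allergic or autoimmune, more than 30 days after infusion 3 | 0/6, enrol more | 2/6, over limit | 0/6 | 2/6, halt |
| D. Grade 3 listed-organ toxicity meeting 8.2.3 | 2/6, suspend | 2/6, over limit | 0/6 | 2/6, halt |

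Correcting 5.1.2 cures D. It does not cure A, B or C, where 5.1.3 and Section 11 still differ.

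**4. Timing of case C.** On schedule, infusion 3 is on day 57 (Study Calendar). The 30-day window ends on day 57 + 30 = 87. Recording, taken from the last infusion, runs to about day 57 + 60 = 117. The gap is days 88 to about 117.

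The interim analysis follows enrolment of six patients (11.5), at 1-2 per month (11.6). Assume even spacing, a 30.44-day month and first infusion on entry.

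- At 2 per month, patient 6 enters 5 × 15.22 = 76 days after patient 1, who is then at about day 77. Nobody has reached day 88.
- At 1 per month, patient 6 enters 5 × 30.44 = 152 days after patient 1. Patients 1 to 3 are then at about days 153, 123 and 92.

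Case C can therefore alter the final verdict, but alters expansion only if the events occur before that decision.

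**5. How much the choice of event can matter.** The documents do not give the share f of patients with grade 3-4 toxicity who also have a DLT. Assume f from 0.25 to 0.75 and every DLT also a grade 3-4 event. The DLT rate is then f × the grade 3-4 rate, and P(Section 11 stops, DLT rule continues) is the difference of the two stopping probabilities. At a 40% grade 3-4 rate:

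| f | DLT rate | P(DLT rule stops) | P(rules disagree) = 76.7% − P(DLT rule stops) |
|---|---|---|---|
| 0.75 | 30% | 58.0% | 18.7% |
| 0.50 | 20% | 34.5% | 42.2% |
| 0.25 | 10% | 11.4% | 65.2% |

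(Differences use unrounded values.) At a 10% grade 3-4 rate, disagreement runs from 4.5% (f = 0.75) to 10.5% (f = 0.25).

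**The case against.** The best defence is that 5.1.2 and 5.1.3 sit together as two branches of one rule, so a sensible reader would take all the wordings to mean DLT. Other provisions also limit the harm. Section 11.3.2 says the trial stops, 5.6.1 lets the investigator discontinue a patient, 8.5.2 provides for discontinuing all investigations if the risk is judged unreasonable, and the STRC can suspend the trial. Part of this stands: harm during conduct is limited. But apart from 11.3.2, itself one of the competing rules, these are case-by-case judgements, and none says which count decides expansion or tolerability.

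It can also be argued that Section 11 means toxicity attributable to treatment, as 7.3 does when describing earlier experience. That reading would shrink cases A and C. It is not stated, and it would supply neither the organ list nor the time window, nor bring in grade 5.

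Three stronger readings are tempting and not supported:

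- **That dosing would continue after two grade 3 DLTs.** This needs the literal 5.1.2, probably a slip for grade 3 or greater, and 5.1.2 is not the only provision that can end dosing, since 8.5.2 can too.
- **That a firm ceiling can be put on patients with infusions outstanding when the rules diverge.** Section 5.1.1 allows delays of up to 3 weeks, so a count based on the 56 days between infusions 1 and 3 (day 1 to day 57) is not an upper bound.
- **That late organ toxicity always splits the expansion decision.** That depends on accrual speed and on when the decision is taken. Section 11.6 implies a pause in accrual after six patients but gives no length.

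**Conclusion.** The inconsistency is real and sits in the primary safety rule. Expansion (5.1.3 against 11.3.2) and the tolerability verdict (11.4.1) can go opposite ways on the same patients, in both directions: Section 11 is stricter in cases A and C, DLT is stricter in case B. The 5.1.2 wording adds to this but is not the core of it.

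How often the rules would part cannot be derived from the documents. The range in step 5 rests on an assumed f. Case A assumes that haematologic events reach grade 3-4: 7.3 names lymphopenia and anemia without grades and reports no attributable grade 3 or 4 toxicity so far. Case B assumes that the deaths carry no separately recorded grade 3-4 event. A reader might infer that the 11.4% and 76.7% are miscalculated; they are not, but they need to be attached to the event that the rule counts.

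**What to change.** Use DLT as defined in 8.2, grade 5 included and counted per patient, as the single event in the synopsis, 5.1.2, 5.1.3, 11.3.2 and 11.4.1. Reword 5.1.2 as: *If >1/6 patients have a DLT, enrolment and further APN401 dosing stop pending assessment of the risk.* State the stage 1 probabilities (11.4% and 76.7%) for true DLT rates of 10% and 40%. Report all grade 3-5 events descriptively.

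The cost is wording in five places, with no new data and no change to the boundary, the sample size or the scope of 8.2. There is a real downside. Grade 3-4 events outside 8.2, such as haematologic toxicity or organ toxicity after the 30-day window, would no longer count towards the Section 11 verdict, although they would still be reported. The sponsor should accept that knowingly.

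The overall (two-stage) percentages in 11.3.2 and 11.4.1 are a separate matter. They carry no weight here and should be checked before being restated for DLT.

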5.6 Duration of therapy

Patients will receive protocol therapy unless:

- 5.6.1 Extraordinary medical circumstances: If at any time the constraints of this protocol are detrimental to the patient's health, protocol treatment should be discontinued. This includes any clinical adverse event, laboratory abnormality or intercurrent illness which, in the opinion of the investigator, indicates that continued treatment with study therapy is not in the best interest of the subject.

Safety and Immunologic Activity of Multiple Infusions of APN401

Wake Forest Baptist Comprehensive Cancer Center

CCCWU 03716

- 5.6.2 Patient withdraws consent
- 5.6.3 Pregnancy: All WOCBP should be instructed to contact the investigator immediately if they suspect they might be pregnant (e.g., missed or late menstrual period) at any time during study participation. Pregnancy tests should be conducted as clinically indicated.
- 5.6.4 Disease progression: Patients who progress clinically before week 9 will be removed from study if other therapy (surgery, radiation, chemotherapy) is needed urgently.

When a patient is removed from study, the Off-Study Form/Early Termination must be completed within seven days.

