8.5 FDA reporting requirements

IND sponsors are responsible for compliance with the Federal Food, Drug, and Cosmetic Act and the implementing regulations (Title 21 of the Code of Federal Regulations). Those responsibilities include: (1) reporting any unexpected fatal or life threatening adverse experience associated with use of the drug by telephone or fax no later than 7 calendar days after initial receipt of the information [21 CFR 312.32(c)(2)]; (2) reporting any adverse experience associated with use of the drug that is both serious and unexpected in writing no later than 15 calendar days after initial receipt of the information [21 CFR 312.32(c)(1)]; and (3) submitting annual progress reports (21 CFR 312.33).

8.5.1 Sterility failure, result of investigation of the cause and any corrective actions, must be reported in an information amendment submitted to the FDA in a timely manner, within 30 calendar days after initial receipt of the positive culture test (21 CFR 312.31). If the patient experiences any serious and unexpected adverse experience that could be from administration of the sterility failure of the cellular product, then this information must be reported to the FDA in an IND safety report no more than 15 calendar days after the initial receipt of the information (21 CFR 312.32).

Safety and Immunologic Activity of Multiple Infusions of APN401
Wake Forest Baptist Comprehensive Cancer Center
CCCWU 03716

8.5.2 If study stopping rules are met and if it is determined that the investigational drug presents an unreasonable and significant risk to subjects, all investigations are to be discontinued and the FDA, all Institutional Review Boards, and all investigators need to be notified (21 CFR 312.56(d)).

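### At more than 3/12 DLTs the protocol suspends enrolment but does not automatically hold infusions, and the stage-1 hold in 5.1.2 uses a different trigger

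*Combined protocol and SAP*

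**What the plan says.** Section 5.1.3 states, for DLT at both boundaries: "Enrollment will be suspended if >1/6 or >3/12 patients manifest DLT". The treatment plan in the synopsis gives the same rule. Neither mentions infusions.

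The only mandatory stop to dosing is in 5.1.2. Its action is that "further enrollment of study subjects and further administration of the study agent will stop pending assessment of the risk". It covers the first six patients only, and its trigger reads "Should >1/6 subjects experience greater than grade 3 or 4 toxicity", not DLT as defined in 8.2.

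Other clauses allow dosing to be held or ended, but none is automatic:

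- 5.1.1: "Leukapheresis and administration of APN401 can be delayed up to 3 weeks", at the physician's discretion.
- 5.6.1: an individual patient stops if, in the investigator's opinion, an event "indicates that continued treatment with study therapy is not in the best interest of the subject".
- 8.5.2: investigations are discontinued "If study stopping rules are met and if it is determined that the investigational drug presents an unreasonable and significant risk to subjects". Both conditions must be met.
- Appendix C: the STRC may suspend the trial while it investigates.

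Sections 11.3.2 and 11.4.1 use a further wording, grade 3-4 toxicity. They give a tolerability verdict and no dosing action.

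**The concern.** Each patient is due three infusions four weeks apart, and the safety of repeated infusions is the primary objective. When a fourth patient has a DLT, the count has passed the limit at which 11.4.1 (worded as grade 3-4 toxicity) still calls APN401 tolerable. The people most directly exposed are those with infusion 2 or 3 still to come.

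Suspending enrolment does nothing for them. If the boundary is judged only on all 12 patients, enrolment is over by then. If it is a running count, enrolment is often, though not always, over at the fourth DLT. Followed as written, scheduled infusions may go ahead while the signal is assessed, unless someone uses a discretionary clause.

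The STRC route has its own gap. Section 8.3 and Appendix C require reports of unexpected grade 4 events, all grade 5 events and grade 3-5 infusion reactions. Other grade 3 organ toxicity counts as a DLT under 8.2.3 but need not be reported to the STRC.

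**Working it through.** **1. The rules side by side.**

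| Boundary | Section | Trigger | Stops enrolment | Stops infusions |
|---|---|---|---|---|
| >1/6 | 5.1.2 | beyond grade 3 or 4 toxicity | yes | yes |
| >1/6 | 5.1.3, synopsis | DLT | yes | not stated |
| >3/12 | 5.1.3, synopsis | DLT | yes | not stated |

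Read literally, the 5.1.2 trigger is grade 5 only. Read as probably meant, it is any grade 3-4 toxicity, without the organ list, exclusions and 30-day window of 8.2.3.

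**2. The plan's own figures.** With X binomial:

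- Stage 1, P(X ≥ 2 | n = 6): 11.4% at a 10% rate and 76.7% at 40%. Both match 11.4.1.
- Stage 2, P(X ≥ 4): 2.6% and 77.5% with n = 12; 1.28% and 61.8% with n = 10. The stated 1.2% and 62% are in effect the figures for 10 patients. That agrees with the additional four patients in 5.1.3 (6 + 4 = 10) but not with the stated total of 12, so both sizes are carried below.

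These stage-2 figures ignore the need to pass stage 1 first, so they are not the chance of reaching this boundary.

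**3. Chance of passing stage 1 and then reaching a fourth DLT (exact).**

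P = Σ over k = 0, 1 of P(Bin(6, p) = k) × P(Bin(n₂, p) ≥ 4 − k), with n₂ = 6 or 4.

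At p = 0.4, n₂ = 6: 0.046656 × 0.1792 + 0.186624 × 0.45568 = 0.0084 + 0.0850 = 0.0934.

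| True rate | 12 patients | 10 patients |
|---|---|---|
| 10% | 0.6% | 0.1% |
| 20% | 4.3% | 1.1% |
| 30% | 8.6% | 2.6% |
| 40% | 9.3% | 3.5% |

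**4. Is enrolment already complete? A floor that needs no timing assumption.** If the fourth DLT patient in enrolment order is the last patient, enrolment must be complete when the fourth DLT occurs. At p = 0.4 with 12 patients: (0.046656 × 0.2304 × 0.4 + 0.186624 × 0.3456 × 0.4) / 0.0934 = 0.0301 / 0.0934 = 32%. With 10 patients it is 66%. At p = 0.1 the figures are 48% and 74%.

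**5. Is anyone still due an infusion? (simulation, conditional on crossing).** From the documents: accrual of 1–2 patients per month (11.6), infusions four weeks apart (days 0, 28 and 56 from the first), and a 30-day DLT window (8.2.3). Assumed, because the documents do not say: equal risk per infusion, 1 − (1 − p)^(1/3); onset uniform over 30 days; a pause after patient 6 of 0 or 87 days (day 57 plus 30 days); no withdrawals. Counted at the fourth DLT: any enrolled patient so far DLT-free with an infusion still due. Ranges cover both accrual rates and both pauses.

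| True rate | Share of crossings, 12 | Share of all trials, 12 | Share of crossings, 10 | Share of all trials, 10 |
|---|---|---|---|---|
| 10% | 46–55% | about 0.3% | 25–31% | 0.03–0.04% |
| 20% | 49–59% | 2.1–2.6% | 27–33% | 0.3–0.4% |
| 30% | 53–63% | 4.5–5.4% | 28–35% | 0.7–0.9% |
| 40% | 56–68% | 5.2–6.3% | 30–38% | 1.0–1.3% |

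Share of all trials = share of crossings × the probability in step 3.

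**6. Both together: enrolment complete and an infusion still due.**

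- At 40%: 37–56% of crossings with 12 patients, i.e. 3.5–5.2% of all trials; 30–38% with 10, i.e. 1.0–1.3%.
- At 20%: 37–51% with 12, i.e. 1.6–2.2% of all trials; 26–33% with 10, i.e. 0.3–0.4%.

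**7. Sensitivity at 40%.**

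- Moving all DLTs from infusion 1 to infusion 3 widens the share of crossings with an infusion still due to 40–86% (12) or 13–78% (10). Enrolment complete then ranges over 32–96% or 65–99.7%.
- If 20% of DLT-free patients leave before each of infusions 2 and 3, an infusion is still due in 47–59% (12) or 24–30% (10) of crossings. With 12 patients the joint event in step 6 falls to about 32–49% of crossings, or 3.0–4.6% of all trials.

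**The case against.** The strongest reply is that this is rare and that a careful investigator would pause dosing anyway. The single-infusion study in 1.4 reported no DLT, so the low rates may be the more likely ones, and at 10% the boundary is reached in under 1% of trials. That stands as to size. It is only partial reassurance, because repeated infusions are what this trial tests. It also does not explain why the hold is mandatory at stage 1 and left to discretion at stage 2.

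Oversight is also wider than the STRC. Section 8.4 requires prompt reporting of adverse events and unanticipated problems to the IRB, and 8.5 requires serious unexpected events to go to the FDA within 15 days (7 if fatal or life-threatening). A DLT that need not be reported to the STRC can therefore still reach outside bodies. That is correct, but these are reporting duties and do not hold an infusion.

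A hold has a cost too. Delay is capped at 3 weeks in 5.1.1, a missed infusion means another leukapheresis (5.5.2), and a long hold could end treatment for some patients or disturb the week-9 immune comparison. This stands, but it applies equally to the hold already written in 5.1.2.

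Finally, the trigger mismatch can be seen as a separate matter of endpoint definition. It belongs here only because endpoint and action must agree at both boundaries for the rule to work.

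**Conclusion.** The concern holds. It rests on the wording and not on any simulated figure: at more than 3/12 the stated action is suspension of enrolment, no section makes a dosing hold automatic there, and the stage-1 hold has a different trigger.

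The size is small. The crossing probabilities in step 3 are exact under binomial sampling. The shares with an infusion still due depend on assumed DLT timing, pause and withdrawals, and vary widely with timing. This is a low-cost patient-safety clarification that should be made. It does not undermine the trial's conclusions.

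**What to change.** In 5.1.3 and the synopsis, state that if more than 1 of the first 6 patients, or a fourth patient at any time, has a DLT, both enrolment and further administration of APN401 stop until the risk has been assessed. State also that this is a study stopping rule for the purposes of 8.5.2. Reword the 5.1.2 trigger as the same DLT endpoint, or merge 5.1.2 into 5.1.3, so that endpoint and action match at both boundaries. The words about a fourth patient at any time also settle that the count is a running one.

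The cost is one sentence in each place and one reworded trigger, with no change to sample size, data collection or analysis. The downside is a possible pause, or lost infusions if it outlasts the 3-week limit, for the last few patients on treatment in the small share of trials that cross. A line on how dosing resumes after a hold longer than 3 weeks would serve both boundaries.
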